5 STUDY ACTIVITIES

5.1 Eligibility Criteria

Subjects must meet all of the following criteria in order to be included in the study. Anything other than a positive response to the questions below will result in exclusion from study participation.

Consent

- ✔ 1. Subjects or their legally authorized representative must voluntarily **sign and date an informed consent**, approved by an independent ethics committee (IEC)/institutional review board (IRB), prior to the initiation of any screening or study-specific procedures.

Demographic and Laboratory Assessments

- ✔ 2. Subjects have completed Study M16-063 (i.e., the preceding study of ABBV-105 and ABBV-599) and have not developed any laboratory or clinical discontinuation criteria as defined in that study.

Relevant Study M16-063 eligibility requirements applicable to Study M16-763 are as follows:

- a. Subjects or their legally authorized representative must voluntarily **sign and date an informed consent**, approved by an independent ethics committee (IEC)/institutional review board (IRB), prior to the initiation of any screening or study-specific procedures.
- b. Adult **male or female**, at least 18 years old.
- c. **Laboratory values** not meeting toxicity management criteria from the Study M16-063 study:
- d. Diagnosis of RA for ≥ 3 months based on the 2010 ACR/European League Against Rheumatism (EULAR) classification criteria for RA.
- e. No history of any of the following cardiovascular conditions:
 - Moderate to severe congestive heart failure (New York Heart Association Class III or IV).
 - Recent history (within past 6 months) of cerebrovascular accident (CVA), myocardial infarction, and/or coronary stenting.
 - Uncontrolled hypertension as defined by a persistent systolic blood pressure (BP) > 160 mmHg or diastolic BP > 100 mmHg. For subjects with known hypertension, the

subject's BP must be stable for at least 4 weeks on current, stable anti-hypertensive medications.

- Prior unprovoked deep vein thrombosis or pulmonary embolism (PE) (i.e., any spontaneous event not directly attributable to trauma or vascular instrumentation).
 - Any other condition which, in the opinion of the Investigator, would put the subject at risk by participating in the protocol.
- f. No history of any arthritis with onset prior to age 17 years or current diagnosis of inflammatory joint disease other than RA (including but not limited to gout, systemic lupus erythematosus, psoriatic arthritis, axial spondyloarthritis including ankylosing spondylitis and non-radiographic axial spondyloarthritis, reactive arthritis, overlap connective tissue diseases, scleroderma, polymyositis, dermatomyositis, fibromyalgia [currently with active symptoms], or any arthritis with onset prior to age 17 years). Current diagnosis of secondary Sjogren's Syndrome is permitted.
- g. Must not have been treated with any investigational drug, other than those supplied in Study M16-063, within 30 days or five half-lives of the drug (whichever is longer) prior to the first dose of study drug or is currently enrolled in another clinical study, other than Study M16-063.
- h. Females must not be pregnant, breastfeeding, or considering becoming pregnant during the study or for approximately 30 days after the last dose of study drug.
- i. For all females of child-bearing potential: a **negative serum pregnancy test** at the Screening Visit and a negative urine pregnancy test at baseline prior to the first dose of study drug in the Study M16-063 study as well as persistently negative urine pregnancy test throughout Study M16-063 and at entrance into this study.
- j. Female subjects of childbearing potential must practice at least 1 protocol-specified **method of birth control** that is effective from Study Day 1 through at least 30 days after last dose of study drug. Female subjects of non-childbearing potential do not need to use birth control.
- k. Must not have any active or recurrent viral infection that, based on the Investigator's clinical assessment, makes the subject an unsuitable candidate for the study, including hepatitis B virus (HBV) or hepatitis C virus (HCV), recurrent or disseminated (even a single episode) herpes zoster, disseminated (even a single episode) herpes simplex, or human immunodeficiency virus (HIV).
- Active HBV, HCV, and HIV are defined as:
- HBV: Hepatitis B surface antigen (HBs Ag) positive (+) or, for hepatitis B core antibody (HBc Ab) positive subjects, detection of HBV DNA by polymerase chain reaction (PCR);
- HCV: HCV RNA detectable in any subject with anti-HCV antibody (HCV Ab);
- HIV: Confirmed positive anti-HIV antibody (HIV Ab) test.
- l. Must not have active TB or meets TB exclusionary parameters (defined as the presence of active TB or latent TB not adequately treated as per protocol requirements).
- m. Must not have used known strong cytochrome P450 (CYP)3A or CYP1A2 inhibitors or strong CYP3A or CYP1A2 inducers from Screening through the end of the study.

- n. Must not have had receipt of any live vaccine within 4 weeks prior to the first dose of study drug, or expected need of live vaccination during study participation including at least 4 weeks after the last dose of oral study drug.
- o. Must not have a history of any malignancy except for successfully treated non-melanoma skin cancer (NMSC) or localized carcinoma in situ of the cervix.
- p. Must not have a history of clinically significant (per Investigator's judgment) drug or alcohol abuse within the last 6 months.
- q. Must not have a history of gastrointestinal perforation (other than appendicitis or penetrating injury), diverticulitis or significantly increased risk for gastrointestinal perforation per investigator judgment.
- r. Must not have any conditions that could interfere with drug absorption including but not limited to short bowel syndrome.
- s. Must not be a recipient of an organ transplant.
- t. Must not have history of clinically significant medical conditions or any other reason that in the opinion of the Investigator would interfere with the subject's participation in this study or would make the subject an unsuitable candidate to receive study drug.
- u. Must not have had an active infection(s) requiring treatment with parenteral anti-infectives within 30 days, or oral anti-infectives within 14 days prior to the first dose of study drug.
- v. Must not have a history of an allergic reaction or significant sensitivity to constituents of the study drugs (and its excipients) and/or other products in the same class.
- w. Subjects must have been treated for ≥ 3 months with ≥ 1 bDMARD therapy but continue to exhibit active RA or had to discontinue due to intolerability or toxicity, irrespective of treatment duration.
- x. Subjects must have been receiving csDMARD therapy ≥ 3 months prior to Study M16-063 baseline visit.

The following csDMARDs are allowed: oral or parenteral methotrexate (MTX) (7.5 to 25 mg/week), sulfasalazine (≤ 3000 mg/day), hydroxychloroquine (≤ 400 mg/day), chloroquine (≤ 250 mg/day), and leflunomide (≤ 20 mg/day).

A combination of up to two background csDMARDs is allowed EXCEPT the combination of MTX and leflunomide.

- y. Subjects must have discontinued all bDMARDs prior to the first dose of study drug. The washout period for bDMARDs prior to the first dose of study drug is specified below or should be at least five times the mean terminal elimination half-life of a drug:
 - ≥ 4 weeks for etanercept;
 - ≥ 10 weeks for adalimumab, infliximab, certolizumab, golimumab, tocilizumab, and abatacept;
 - ≥ 1 year for rituximab OR ≥ 6 months if B cells have returned to pretreatment level or normal reference range (central lab) if pretreatment levels are not available.

- z. Subjects must have discontinued all high-potency opiates at least 1 week and oral traditional Chinese medicine for at least 4 weeks prior to the first dose of study drug (refer to Section 5.3 for prohibited medications).
- ✔ 3. Subject is willing and/or able to comply with procedures required in this protocol.

Concomitant Medications

- ✔ 4. Subject must not be currently enrolled in any study (except the preceding Study M16-063) or planning to enroll in another interventional clinical study while participating in this study.
- ✔ 5. Subject must not require vaccination with any live vaccine during study participation, including at least 30 days after the last dose of study drug.

5.2 Contraception Recommendations

Contraception Requirements for Females

Subjects must follow the following contraceptive guidelines as specified:

- Females, Non-Childbearing Potential

Females do not need to use birth control during or following study drug treatment if considered of non-childbearing potential due to meeting any of the following criteria:

- Postmenopausal, age > 55 years with no menses for 12 or more months without an alternative medical cause.
- Postmenopausal, age ≤ 55 years with no menses for 12 or more months without an alternative medical cause AND a follicle-stimulating hormone (FSH) level > 40 IU/L.
- Permanently surgically sterile (bilateral oophorectomy, bilateral salpingectomy, or hysterectomy).

- Females, of Childbearing Potential

Females of childbearing potential must avoid pregnancy while taking study drug(s) and for at least 30 days after the last dose of study drug. Females must commit to one of the following methods of birth control:

- Combined (estrogen and progestogen containing) hormonal birth control (oral, intravaginal, transdermal, injectable) associated with inhibition of ovulation initiated at least 1 month prior to study Baseline Day 1.
- Progestogen-only hormonal birth control (oral, injectable, implantable) associated with inhibition of ovulation initiated at least 1 month prior to study Baseline Day 1.
- Bilateral tubal occlusion/ligation (can be via hysteroscopy, provided a hysterosalpingogram confirms success of the procedure).
- Intrauterine device (IUD).
- Intrauterine hormone-releasing system (IUS).

- To have a vasectomized partner(s) (the vasectomized partner[s] has received medical assessment of the surgical success and is the sole sexual partner of the trial subject).
- To practice true abstinence (if acceptable per local guidelines), defined as: Refraining from heterosexual intercourse when this is in line with the preferred and usual lifestyle of the subject (periodic abstinence [e.g., calendar, ovulation, symptothermal, post-ovulation methods] and withdrawal are not acceptable).

If required per local practices, male or female condom with or without spermicide OR cap, diaphragm, or sponge with spermicide should be used in addition to one of the highly effective birth control methods listed above (excluding true abstinence). A condom is required in the following countries: UK, Germany, and Spain.

Concomitant conventional synthetic disease-modifying antirheumatic drugs (csDMARDs) (i.e., MTX, sulfasalazine, etc.) have been prescribed per standard of care prior to study entry and are allowed to be continued during the study. Contraception should continue while the subject is on the concomitant csDMARD(s) and that duration of contraception after discontinuation of the csDMARD(s) should be based on the local label. Additional local requirements may apply.

5.3 Prohibited Medications and Therapy

JAK Inhibitor

Initiation of any new JAK inhibitors (including, but not limited to, tofacitinib [Xeljanz®], baricitinib [Olumiant®], and filgotinib) is not allowed.

Corticosteroids

Oral corticosteroids > 10 mg prednisone/day or equivalent and intra-articular, intramuscular, intravenous, trigger point or tender point, intra-bursa, and intra-tendon sheath corticosteroids are NOT allowed during this study except as described in Section 5.4 (Prior and Concomitant Therapy) for treatment of an RA flare, as defined by the investigator.

Any csDMARD/Immunosuppressive Therapy Not Listed in Section 5.4 (Prior and Concomitant Therapy)

All biologic therapies are prohibited during the study. Examples of biologic therapies include but are not limited to the following:

- Humira® (adalimumab)
- Enbrel® (etanercept)
- Remicade® (infliximab)
- Kineret® (anakinra)
- Rituxan® (rituximab)
- Cimzia® (certolizumab pegol)
- Simponi® (golimumab)

- Actemra® (tocilizumab)
- Raptiva® (efalizumab)
- Tysabri® (natalizumab)
- Stelara® (ustekinumab)
- Benlysta® (belimumab)
- Orencia (abatacept)

Strong CYP3A or CYP1A2 Inhibitors or Inducers

Systemic use of known strong inhibitors or inducers of CYP3A or CYP1A2 is excluded from the Screening Visit through the end of the study. The most common strong CYP3A or CYP1A2 inhibitors and inducers are listed in [Table 1](#).

Table 1. Examples of Commonly Used Strong CYP3A or CYP1A2 Inhibitors and Inducers

Strong CYP3A Inhibitors	Strong CYP3A Inducers
Boceprevir Cobicistat Clarithromycin Conivaptan Grapefruit (fruit or juice) Indinavir Itraconazole Ketoconazole Lopinavir/Ritonavir Mibefradil Nefazodone Nelfinavir Posaconazole Ritonavir Saquinavir Telaprevir Telithromycin Troleandomycin Voriconazole	Carbamazepine Phenytoin Rifampin Rifapentine St. John's Wort
Strong CYP1A2 Inhibitors	Strong CYP1A2 Inducers
Fluvoxamine Ciprofloxacin Enoxacin Zafirlukast	Rifampin

Live Vaccines

Use of live vaccines is prohibited during the study and must be avoided for four weeks after the last dose of study drug. Examples of live vaccines include, but are not limited to, the following:

- Monovalent live influenza A (H1N1) (intranasal);
- Seasonal trivalent live influenza (intranasal);
- Herpes zoster;
- Rotavirus;
- Varicella (chicken pox);
- Measles-mumps-rubella or measles mumps rubella varicella;
- Oral polio vaccine;
- Smallpox;
- Yellow fever;
- Bacille Calmette-Guérin (BCG);
- Typhoid.

5.4 Prior and Concomitant Therapy

Subjects should continue on their previous background csDMARD therapy from Study M16-063, restricted to the following: oral or parenteral methotrexate (7.5 to 25 mg/week), sulfasalazine (≤ 3000 mg/day), hydroxychloroquine (≤ 400 mg/day), chloroquine (≤ 250 mg/day), and/or leflunomide (≤ 20 mg/day). Combinations of up to two csDMARDs are allowed except for the combination of MTX and leflunomide.

At any time, the csDMARD dose may be decreased for safety reasons. Subjects taking MTX should take a dietary supplement of oral folic acid (or equivalent, such as folinic acid) throughout study participation. Folic acid dosing and timing of regimen should be followed according to Investigator's instructions. AbbVie will not provide the csDMARDs (or folic acid, if taking MTX).

Subjects should continue on their stable doses of nonsteroidal anti-inflammatory drugs (NSAIDs), acetaminophen/paracetamol, oral corticosteroids (equivalent to prednisone ≤ 10 mg/day), or inhaled corticosteroids.

- If taking any of the above on a scheduled basis, subjects should continue to take them as they did at study entry with no change in dose or frequency, including on study visit days.
- If subject was not taking any of the above at baseline, these must not be initiated except where permitted by protocol (i.e., after Week 18).
- If taking any of the above, including low-potency analgesics (i.e., tramadol, codeine, hydrocodone, or propoxyphene) at baseline on an as-needed (PRN) basis, subjects should continue to use them for the same reason and same dose each time, but they should not be taken within the 24 hours prior to any study visit to avoid bias in outcome measurements.

Calculation of the Clinical Disease Activity Index (CDAI) is required to determine if a subject fails to achieve LDA. Calculation of CDAI will be performed at the Week 18 visit by Interactive Response

Technology (IRT) with input from site personnel on joint counts and PtGA and PhGA score. The calculation used to determine CDAI score at Week 18 is as follows:

$$\text{CDAI} = \text{TJC28} + \text{SJC28} + \text{PtGA (cm)} + \text{PhGA (cm)}$$

Beginning at Week 18, subjects who fail to achieve $\text{CDAI} \leq 10$ should have background medication(s) adjusted or initiated. Initiation of or change in corticosteroids, NSAIDs, or acetaminophen, or adding/increasing csDMARD doses (restricted to oral or parenteral MTX, sulfasalazine, hydroxychloroquine, chloroquine, and leflunomide, except for the combination of MTX and leflunomide), is allowed as per local label and at investigator discretion. If necessary, a burst of systemic corticosteroids (maximum dose of 0.5 mg/kg of prednisone or its equivalent) is allowed, after which subject should resume their usual daily oral corticosteroid dose.

Intra-articular, intramuscular, intravenous, trigger point or tender point, intra-bursa, and intra-tendon sheath injections of corticosteroids, at dosage and frequency per standard of care, are allowed after the Week 18 assessments have been performed and at time points thereafter. For the analysis of the TJC and SJC, injected joints will be considered "not assessable" for 3 months from the time of the intra-articular injection.

In the event of tolerability (or other safety) issues, the doses of these medications may be decreased or discontinued with substitution of another permitted medication from that class. PRN use of inhaled corticosteroids is permitted at any time.

Study drug interruption is allowed up to 30 consecutive days. If the subject undergoes elective surgery, the study drug should be interrupted 2 weeks prior to the planned surgery. If the subject must undergo emergency surgery, the study drug should be interrupted at the time of surgery. In either case, study drug may be reintroduced once the physician has examined the surgical site and determined that it has healed and there is no sign of infection.

Any medication or vaccine (including over-the-counter or prescription medicines, vitamins, and/or herbal supplements) that the subject receives during the study should be recorded through the follow-up phone call 30 days after the last treatment visit (Week 60).

Any questions regarding concomitant or prior therapy should be raised to the AbbVie emergency contact. Information regarding potential drug interactions with ABBV-105 or ABBV-599 can be located in the ABBV-105 or upadacitinib Investigator's Brochures.

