5.5 Withdrawal of Subjects and Discontinuation of Study

A subject may voluntarily withdraw or be withdrawn from the study at any time for reasons including, but not limited to, the following:

- Clinically significant abnormal laboratory results or AEs, which rule out continuation of the study drug, as determined by the investigator or the AbbVie Therapeutic Area Medical Director.
- Serious infections (e.g., sepsis) that cannot be adequately controlled within 2 weeks by anti-infective treatment or would put the subject at risk for continued participation in the trial as determined by the Investigator.

- The investigator believes it is in the best interest of the subject.
- The subject requests withdrawal from the study.
- Eligibility criteria violation was noted after the subject started study drug and continuation of the study drug would place the subject at risk.
- Introduction of prohibited medications or dosages and continuation of the study drug would place the subject at risk.
- Subject is non-compliant with tuberculosis (TB) prophylaxis (if applicable) or develops active TB at any time during the study.
- The subject becomes pregnant while on study drug.
- Malignancy, except for localized NMSC or carcinoma in-situ of the cervix.
- Subject is significantly noncompliant with study procedures, which would put the subject at risk for continued participation in the trial.
- Subject develops a gastrointestinal perforation.

In addition, the following discontinuation criteria also apply:

- Subjects not responding to therapy can discontinue study drug (or withdraw from study) at any time for any reason during the study in order to receive standard of care.
- Subjects who demonstrate worsening of joint count (SJC and/or TJC) at 2 consecutive visits (scheduled or unscheduled) should be discontinued from study drug and treated with standard of care at the discretion of the clinician.
- Starting at the Week 18 visit (after the Week 18 assessments have been performed) and at visits thereafter, subjects who fail to achieve at least 20% improvement in TJC and SJC should be discontinued.

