5.6 Follow-Up for Subject Withdrawal from Study

To minimize missing data for efficacy and safety assessments, subjects who prematurely discontinue study drug treatment should continue to be followed for all regularly scheduled visits, unless subjects have decided to discontinue the study participation entirely (withdrawal of informed consent). Subjects should be advised on the continued scientific importance of their data even if they discontinue treatment with study drug early.

Following discontinuation of study drug, the subject should be treated in accordance with the investigator's best clinical judgment irrespective of whether the subject decides to continue participation in the study. In addition, all future rescue- and efficacy-driven discontinuation criteria no longer apply. This includes 20% TJC/SJC calculations at Weeks 12 through 24, Weeks 36 through 40 and Week 48 and thereafter, as well as CDAI calculation at Week 26, if applicable. If at any point a subject no longer wants to provide assessments (withdrawal of informed consent) following discontinuation of study drug, a second PD visit is not required.

If a subject prematurely discontinues study participation (withdrawal of informed consent), the procedures outlined for the PD visit should be completed as soon as possible, preferably within 2 weeks. In addition, if subject is willing, a 30-day follow-up phone call after the last dose of study drug may be completed to ensure all treatment-emergent AEs/SAEs have been resolved.

All attempts must be made to determine the date of the last study drug dose and the primary reason for discontinuation of study drug or study participation. The information will be recorded on the appropriate electronic case report form (eCRF) page. However, these procedures should not interfere with the initiation of any new treatments or therapeutic modalities that the Investigator feels are necessary to treat the subject's condition. Following discontinuation of study drug, the subject should be treated in accordance with the Investigator's best clinical judgment irrespective of whether the subject decides to continue participation in the study.

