## **8.2 Handling of Missing Data**

The analysis will be based on As Observed data, and no imputation will be conducted.

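### Background RA therapy is escalated from Week 18 in subjects above CDAI 10, and later responses are counted As Observed with no rule for it, which confounds the within-arm reading of maintained efficacy

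*Protocol*

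**What the plan says.** Protocol 5.4 keeps background therapy largely stable up to Week 18. From Week 18, subjects who do not reach CDAI of 10 or below "should have background medication(s) adjusted or initiated"; Protocol 5.5 repeats this for later visits. The permitted changes cover corticosteroids, NSAIDs, acetaminophen and added or increased csDMARDs. In addition, "a burst of systemic corticosteroids (maximum dose of 0.5 mg/kg of prednisone or its equivalent) is allowed", and steroid injections by several routes are permitted.

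Some subjects leave study drug instead. Under Protocol 5.5, from Week 18, "subjects who fail to achieve at least 20% improvement in TJC and SJC should be discontinued". Subjects whose joint counts worsen at two consecutive visits should also stop. From Week 24, a subject with 20% joint improvement but CDAI still above 10 is only to be considered for discontinuation, so an escalated subject may remain on study drug.

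On the analysis side, Protocol 3.2 and SAP 3.2 define low disease activity (LDA), remission and ACR20/50/70 by the score, or by change from the M16-063 baseline, alone. SAP 8.2 states: "The analysis will be based on As Observed data, and no imputation will be conducted". SAP 8.5 and 8.6 plan no additional or subgroup efficacy analyses. The one analysis rule tied to escalation is in Protocol 5.4 and 5.5: injected joints are not assessable in the joint-count analysis "for 3 months from the time of the intra-articular injection".

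**The concern.** The CDAI threshold that prompts escalation is the same one that defines an efficacy endpoint. A subject who misses it at Week 18, has background therapy increased and then meets it at Week 24 counts as a responder in the assigned group, with nothing in the table to show the escalation.

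This matters although efficacy is purely descriptive. The clinical hypothesis (Protocol 2.1, SAP 2.1) is that efficacy is maintained, and Protocol 4.2 makes the primary comparison each arm against its own profile in M16-063. Escalation starts inside that before/after comparison. The interim tables in SAP 11 draw on the same endpoints.

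The protocol recognises this kind of bias elsewhere. As-needed analgesics may continue, but "they should not be taken within the 24 hours prior to any study visit to avoid bias in outcome measurements". No comparable provision covers the Week 18 changes in systemic steroids, NSAIDs, acetaminophen or csDMARDs.

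Group 6 (placebo to ABBV-599) is a special case. It starts ABBV-599 at Week 12 and so meets the trigger after about 18 − 12 = 6 weeks on that treatment, against about 18 weeks on treatment in the continuing groups. It is then pooled with Group 1 in Group 7.

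**Working it through.** The plan gives no escalation rate, conversion rate or expected response rate, so there is no figure to reproduce. The check has two parts.

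**1. Does a post-escalation response count?** Take a subject with at least 20% improvement in joint counts and CDAI above 10 at Week 18.
- Protocol 5.5 does not require discontinuation, and 5.4 calls for a background change.
- Suppose CDAI is 8 at Week 24. Protocol 3.2 and SAP 3.2 make this subject a CDAI LDA responder.
- SAP 8.2 and 8.4 use the value as observed, and SAP 8.1 places it in the randomised group.
- The medication table in SAP 7.3 is by generic name and group. As described, it shows neither when a drug was started or increased nor whether a response followed.

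So the response counts, and its link to escalation is not shown.

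**2. How large could the effect be?** All inputs are assumptions:
- p = share in CDAI LDA at Week 18
- s = share of those still in LDA later
- r = share of subjects above the threshold who are escalated, still observed and later in LDA
- d = share of subjects above the threshold who are no longer observed

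As Observed rate = [p·s + (1 − p)(1 − d)·r] / [p + (1 − p)(1 − d)].

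Rate with escalated subjects counted as non-responders, full denominator = p·s.

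With p = 40%, s = 80%, r = 20%, d = 0:
- As Observed: 0.40 × 0.80 + 0.60 × 0.20 = 0.32 + 0.12 = 44%.
- Escalated subjects as non-responders: 0.40 × 0.80 = 32%.

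A fall from 40% to 32% would be shown as a rise to 44%.

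With d = 0 the excess is (1 − p)·r. For p from 20% to 50% and r from 10% to 40%, it runs from 0.50 × 0.10 = 5 points to 0.80 × 0.40 = 32 points.

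The excess depends on how many subjects above the threshold drop out of the data (same p, s and r):

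| d | As Observed, r = 20% | As Observed, r = 0 | Part due to conversion |
|---|---|---|---|
| 0 | 44.0% | 32.0% | 12.0 points |
| 30% | (0.32 + 0.084)/0.82 = 49.3% | 0.32/0.82 = 39.0% | 0.084/0.82 = 10.2 points |
| 60% | (0.32 + 0.048)/0.64 = 57.5% | 0.32/0.64 = 50.0% | 0.048/0.64 = 7.5 points |

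As more of these subjects leave, the part due to escalation shrinks, while the As Observed rate rises for a different reason: missing data. This is why a supplementary row needs a stated denominator.

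**The case against.** The strongest reply is that the As Observed tables are a legitimate description of outcome under study drug with background care adjusted as needed. There is no primary efficacy endpoint and no efficacy test, so no error rate is affected, and the documents nowhere claim that a later response was caused by study drug. This stands as far as it goes. But the tables do not carry that description, and the hypothesis of maintained efficacy invites a reading about the drug itself.

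Stronger readings that a reader might draw are not supported:
- *Every subject above CDAI 10 is escalated and kept on drug.* The rule says should, the choice of change is left to the investigator, and Protocol 5.5 sends clear non-responders to discontinuation.
- *Nothing protects the endpoints.* The injected-joint rule does so in part. It covers joint counts only, and not systemic steroids, NSAIDs, acetaminophen, csDMARDs or the non-joint components.
- *Differences between arms shrink by a known amount.* Between-arm contrast is not the planned primary comparison, and the size rests on invented inputs. With 30% conversion, rates of 50% and 20% become 50 + 50 × 0.3 = 65% and 20 + 80 × 0.3 = 44%, a gap of 21 points instead of 30. If half of the failures stop and stay in the denominator as non-responders, they become 57.5% and 32%, a gap of 25.5.
- *All later response in escalated subjects is due to escalation.* Some may be late response to study drug, particularly in Group 6.

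**Conclusion.** The concern holds as a gap in the analysis plan. For subjects who stay on study drug, escalation from Week 18 is prompted by a threshold that is also an endpoint, and apart from injected joints neither document accounts for it. Response rates from Week 24 can hold or rise because of escalation, so the within-arm comparison behind maintained efficacy is confounded.

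The size cannot be known from the documents. The 44% against 32% is one illustration, and the 5 to 32 points are the span of assumed inputs with no dropout; neither is a forecast. The harm is to interpretation, not to type I error.

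**What to change.** Leave the care rules as they are and amend SAP 8.4:

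1. Keep the As Observed rows, labelled as study drug plus background escalation as needed.
2. Beside them, for DAS28(CRP) LDA and remission, CDAI LDA and remission, and ACR20/50/70, add a supplementary row. In it a subject is a non-responder at visits after the first RA-related start or increase of a corticosteroid, NSAID, acetaminophen or csDMARD at or after Week 18. State the denominator and keep escalated subjects in it.
3. Print the number escalated by group, visit and drug class.
4. Show these rows for Group 6 separately from Group 1, and not only within Group 7.
5. Read any statement on maintained efficacy from both rows together.

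Do not add a summary of continuous endpoints restricted to values before escalation. If the trigger is followed, later means would come mainly from subjects who stayed at CDAI 10 or below, which selects responders and flatters persistence.

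The cost is SAP wording and a few tables. Protocol 7.1 requires the SAP to be final only before database lock, and concomitant therapy is recorded at every visit (Protocol 5.4, Appendix D). There are two downsides. The supplementary row is conservative, since some late responses may be due to study drug and a minor analgesic start counts as failure. RA-related changes must also be flagged in blinded review, after confirming that dose and indication are captured; the text available does not show this.
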